3.10.2.7 Treatment of Missing Data

For the primary endpoint requiring a valid weekly average home BP value preceding the Randomization and Week 12 visits, if a participant does not have a valid endpoint measure, that value will be flagged as missing and requiring imputation. Imputation will also be performed for missing Week 6 results. In all cases it is the BP weekly average that will be imputed for each time interval, not each component measure used to calculate the average. Imputations will be performed separately by analysis set, as required (i.e., Randomized Set, Per Protocol).

For missing Baseline (prior to Randomization) SBP results, missing data are considered missing at random and a multiple imputation will be applied.

For post-Randomization missing data, a Retrieved Data Multiple Imputation will be applied to account for the occurrence of intercurrent events which aligns to the Treatment Policy Strategy for handling of Intercurrent Events:

- 1) Participants with missing Baseline measurements will be assumed to have data missing at random and will have results imputed from the full baseline sample of participants (pre-randomization).
- 2) Participants with missing Week 6 or Week 12 home BP assessments and experiencing intercurrent events will have their result imputed for the primary analysis using multiple imputation. Participants with intercurrent events will have their missing result based on other participants with intercurrent events within the same treatment group.
 - a. Receive Wrong Treatment:
 - i. Participants who received the wrong treatment and have missing Week 12 results will have results imputed from the sample of participants who received the same treatment they received during Period 3. The participants will be grouped as randomized for the primary analysis.
 - ii. Participants who received the wrong treatment and have missing Week 6 results will have results imputed from the sample of participants who received the same treatment they received during Period 2. The participants will be grouped as randomized for the primary analysis.
 - b. Participants with IMP interruption for supply-related reasons will have missing Week 6 or Week 12 results imputed from the sample of participants with intercurrent events and assigned the same randomized treatment.
 - c. Participants with missing Week 12 who do not have up-titration at Week 6 will have results imputed from the sample of participants randomly assigned to the same treatment and have an intercurrent event. Week 6 results will be used to impute the Week 12 timepoint.
 - d. Participants who discontinue treatment for reasons related to study treatment or study procedures will be imputed using a control-based imputation from the sample of participants with intercurrent events and randomly assigned to one of the control groups (AI, TA, TI).
- 2) Participants non-adherent to study treatment:
 - a. Participants who were non-adherent to study treatment during Period 2 with missing Week 6 home BP measurement will be imputed from the sample of participants with intercurrent events and randomly assigned to one of the control groups (AI, TA, TI).
 - b. Participants who were non-adherent to study treatment during Period 3 with missing Week

12 home BP measurements will be imputed from the sample of participants with intercurrent events and randomly assigned to one of the control groups (AI, TA, TI).

3) Participants with missing Week 6 or Week 12 home BP assessments who were adherent to study treatment and did not experience intercurrent events will have their results imputed for the primary analysis using multiple imputation. Participants without intercurrent events will have their missing result based on other participants also without intercurrent events and within the same treatment group.

If there is not a sufficient sample size to perform multiple imputations as described, participants with and without intercurrent events will be included in the source sample for imputation.

Multiple imputation (MI) will be applied, replacing each missing average SBP home assessment with a set of plausible values from the identified subsample, listed above. This will represent the uncertainty of the correct value based on the observed results. The multiply imputed datasets will be analyzed using standard procedures for complete data with their results combined with a variance-adjustment. The multiple imputation will be computed as follows:

- 1) Imputation:
 - a. For missing baseline, a regression method will impute missing data from the overall randomized sample.
 - b. For missing Week 12 SBP results, a regression method will impute missing data from the respective subsample with or without intercurrent events, as specified above, and within the respective treatment group. Imputation will be performed using a Fully Conditional Specification (FCS) model using the regression method and will include the following factors:
 - Age, sex, race, BMI, and ethnicity
 - Patient smoking and alcohol consumption
 - Baseline (at Randomization) average home SBP, Week 6 average home SBP
- 2) Analyzing: The final multiple imputed datasets will be analyzed using Ruben's Rule.

Proc MI and Proc MIANALYZE in SAS will be used to generate the datasets and run the analyses.

Sample SAS Code:

```
PROC MI DATA = SBP OUT = SBP2 SEED = 20231010 NIMPUTE = 100
    MINIMUM = . . . . . . . . 80 80 80
                                        ROUND = . . . . . . . . . . . 1 1 1
     MAXIMUM = . . . . . . . 200 200 200 MINMAXITER = 5000 SIMPLE NOPRINT;
     FCS REG (BASE = TRTPN AGE SEX RACE BMI ETHNIC SMK ALC/ DETAILS);
     FCS REG (SBP6 = TRTPN AGE SEX RACE BMI ETHNIC SMK ALC BASE/ DETAILS)
     FCS REG (SBP12 = TRTPN AGE SEX RACE BMI ETHNIC SMK ALC BASE SBP6/
             DETAILS)
     CLASS TRTPN SEX RACE ETHNIC SMK ALC;
     VAR TRTPN AGE SEX RACE BMI ETHNIC SMK ALC BASE SBP6 SBP12;
    RUN:
*SBP2 will be reformatted into an analysis dataset, here titled ADEFF with
each observation is on a separate line;
*Note that in actual implementation, the imputations will be done separately
for those with intercurrent events and those without intercurrent events.
Note also that baseline values will be imputed from all observations;
PROC MIXED DATA = ADEFF EMPIRICAL METHOD = REML;
      BY IMPUTNUM;
      CLASS SITEID SUBJID VISIT TRTP;
      MODEL AVAL = BASE VISIT TRTP VISIT*TRTP / CL;
```

```
WHERE VISIT IN ('WEEK6','WEEK12');
LSMEANS VISIT*TRTP / DIFF CL ALPHA=0.05;
ODS OUTPUT COVPARMS = CP LSMEANS = LSM DIFF = DIFFS;
RUN;
PROC SORT DATA = DIFF;
BY TRTP _TRTP VISIT _VISIT;
RUN;
PROC MIANALYZE DATA = DIFF ALPHA = 0.05;
BY TRTP _TRTP VISIT _VISIT;
WHERE TRTP = 1 AND _TRTP NE 1 AND VISIT = _VISIT;
*TRTP = 1 corresponds to GMRx2 in this example;
MODELEFFECTS ESTIMATE;
STDERR STDERR;
ODS OUTPUT PARAMETERESTIMATES=SBP_PROP;
RUN;
```

TRTPN is the planned treatment group, SEX is the sex of the participant, RACE is participant race, ETHNIC is participant ethnicity, SMK is participant smoking status, ALC is alcohol use. BASE is the baseline (at Randomization) average SBP value, SBP6 is the average SBP value at Week 6 (Visit 1), and SBP12 is the average SBP value at Week 12 (Visit 2). The minimum and maximum values for SBP imputation may be modified according to the observed minimum and maximum within the sample. If the multiple imputation models cannot converge, model reduction (excluding covariates) may be performed.

For binary endpoints with missing results, a single value imputation of "failure" will be performed for analysis (Section 3.10.1.1).

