8.4.2. Double-Blind Treatment Period

The 4-week single-blind active run-in will be followed by a 12-week double-blind period with randomization to one of the following four treatment groups:

Table 4: Treatment Groups in the Trial

Group	Intervention	N	Treatment
1	Triple - TAI (GMRx2)	600	telmisartan 20 mg/amlodipine 2.5 mg/indapamide 1.25 mg (GMRx2 dose 2). At Week 6 visit, forced up-titration to telmisartan 40 mg/amlodipine 5 mg/indapamide 2.5 mg (GMRx2 dose 3)
2	Dual - TA	300	telmisartan 20 mg/amlodipine 2.5 mg. At Week 6 visit, forced up-titration to telmisartan 40 mg/amlodipine 5 mg
3	Dual - TI	300	telmisartan 20 mg/indapamide 1.25 mg. At Week 6 visit, forced up-titration to telmisartan 40 mg/indapamide 2.5 mg
4	Dual - AI	300	amlodipine 2.5 mg/indapamide 1.25 mg. At Week 6 visit, forced up-titration to amlodipine 5 mg/indapamide 2.5 mg

T=telmisartan, A=amlodipine, I=indapamide

On the day of randomization visit (W0), all participants will be prescribed and dispensed trial medication to be taken between the randomization and Week 6 visit (period 2). On the day of the Week 6 visit, all participants will be prescribed and dispensed trial medication (the same initial treatment but at double dose) to be taken between Week 6 and Week 12 visit (period 3). **All participants will be up-titrated at Week 6**, unless the investigator believes there is a specific contraindication for a particular participant, such as symptomatic hypotension or is asymptomatic with very low home or clinical BP levels (i.e. SBP <100 mmHg). If a participant is asymptomatic but is judged to be not suitable for dose doubling, then they should be continued on existing trial medication at Week 6. For participants who are not up-titrated at Week 6, up-titration can occur after Week 6 and before Week 12, if appropriate. Week 12 visit date should remain unchanged.

Participants should take trial medication once daily in the morning either before or after breakfast immediately after taking home BP measurement.

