10.2.8. Home BP Measurement

For the days on which home BP is measured, BP measurements should be at the same time in the morning and evening on each measurement day during the following time ranges:

1. morning (ideally between 06:00-10:00 hours) – prior to taking trial medication;
2. evening (ideally between 18:00-22:00 hours).

Participants should aim to have at least 6 hours interval between the morning and evening measurements. In the week before the Randomization, Week 6 and Week 12 trial visits, BP measurements should be taken on the 4 days immediately prior to the day of the on-site trial visit. In other weeks, measurements should ideally be performed on a single set day. Each home BP measurement should be done as a triplicate i.e., three individual measurements,, following the protocol outlined in Appendix 3, page 42. Telemonitored BP values will be monitored for adherence with measurement schedules and high values (as noted in Section 8.6, page 22), with reporting to the clinic and for medical management as needed.

Participants eligible for run-in medication will be issued with a home BP monitor at the screening visit and will be asked to bring it with them to the randomization visit. If they continue to randomization, they will continue to use the same home BP monitor.

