2.2.3 Trial design

The trial design is described in detail in Section 7 of the protocol, with the following figure summarising the overall design:

0				-	-	
		Period 1	Period 2	Period 3	Period 4	
		Single-blind run-in	Double-blind	Double-blind	Safety FU]
Screening		GMRx2 Dose 2	GMRx2 Dose 2 T 20 / A 2.5 T 20 / I 1.25 A 2.5 / I 1.25	GMRx2 Dose 3 T 40 / A 5 T 40 / I 2.5 A 5 / I 2.5	Non-trial treatment	
Visit	RI	F	۲ F	5U1 F	02	EOT
Visit No.	V1	V	/2	V3	V 4	V5
Week	-4		0	6	12	16

GMRx2 Dose2 = T 20 / A 2.5 / I 1.25; GMRx2 Dose3 = T 40 / A5 / I 2.5; T = telmisartan; A = amlodipine; I = indapamide; RI = run-in; R = randomization; FU = follow-up; EOT = end of trial; V = visit; Forced up-titration at FU1; EOT will be telephonic.

Of particular note are the two study visits Week 6/Follow-up 1 (FU1) and Week 12/Follow-up 2 (FU2). Preceding both visits, participants will be requested to perform extra home BP measurements in the week running up to the clinic visit. At FU1, all participants are expected to be up-titrated to the higher level of study drug, unless there is a specific contraindication, such as symptomatic hypotension. At FU2, the participant will complete the double-blinded part of the trial and continue on non-trial treatment in a safety follow-up period. Although time periods have been nominated (6 weeks for FU1 and 12 weeks for FU2) these are indicative only and actual time periods may vary within an expected window, as specified within the study protocol.

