Table 3-3 Definitions of Home Blood Pressure Derivations

	 Sessions containing three or more BP measures will be prioritised over those with two. Those with only one BP measure will be used as a last resort. If the first step does not uniquely select one session for the period, the earliest session of those selected in the first step will be used.
Calculation of averages	 To calculate an average, perform a simple, unweighted mean of the flagged BP measurements in the selected sessions for the period of interest. At Randomization: A minimum of 6 measures (e.g. ≥2 sets of triplicate measures or ≥3 sets of duplicate measures) are expected, including at least 1 morning and 1 evening, each with ≥2 measures per protocol-specified eligibility criteria. Post-Randomization: At least 4 consecutive calendar days (8 measurement sessions, 24 BP readings) were recommended. Calculations: For all timepoints, calculations of averages will be performed if there is at least 1 valid BP measurement. The home BP values for the purpose of Baseline, FU visit 1 Week 6 and FU visit 2 Week 12 are averages (as defined above) across up to 7 calendar days immediately preceding each in-clinic visit. Each of the up to 2 selected sessions per day (1 morning and 1 evening) may be included in the calculation. Days with no valid measures reported will be excluded from the calculation (i.e., only days with SBP measurements recorded will be included in average).

In addition, for descriptive plots of SBP and DBP measurements post-randomization, weekly average BP will be computed where Week is defined in relation to the randomization date with Week 1 initiating on Day 1, the first treatment with randomized trial medication:

Week = (date of BP measurement - date of first dose of randomized treatment)/7Week is rounded up to the nearest integer. Averages will otherwise be calculated in the same manner as described in Table 3-3.

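### Missing Week 12 home SBP is imputed without the participant's own blood pressure after the Week 6 dose doubling, although the trial collects it

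*SAP*

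**What the plan says.** **Imputation model.** SAP 3.10.2.7 lists the factors for a missing Week 12 value: "Age, sex, race, BMI, and ethnicity", smoking, alcohol, and "Baseline (at Randomization) average home SBP, Week 6 average home SBP". The sample code has the same terms plus planned treatment: "FCS REG (SBP12 = TRTPN AGE SEX RACE BMI ETHNIC SMK ALC BASE SBP6". Values are drawn "from the respective subsample with or without intercurrent events, as specified above, and within the respective treatment group". Participants who stop treatment for treatment- or procedure-related reasons, and non-adherent participants, are instead imputed from control-arm donors with intercurrent events.

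**Timing.** Under SAP Table 3-3 each home average is taken "across up to 7 calendar days immediately preceding each in-clinic visit". SAP 2.2.3 states "At FU1, all participants are expected to be up-titrated to the higher level of study drug", and Protocol 8.4.2 describes the Period 3 supply as "the same initial treatment but at double dose". The Week 6 average therefore ends before the dose changes.

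**What else is recorded after FU1.** Protocol 10.2.7 has clinic BP measured at all scheduled visits, and the schedule of evaluations includes Week 12. For weeks outside the endpoint windows, Protocol 10.2.8 says: "In other weeks, measurements should ideally be performed on a single set day". Protocol Appendix 3 has home readings sent automatically to the trial database. The SAP already computes weekly home averages, for descriptive plots.

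**Other handling.** Clinic SBP replaces a missing home value in one supplemental complete-case analysis (SAP 3.10.1.1, item 3). The tipping point analysis in SAP 3.10.2.8 is optional and fixes the shift in the control arms at 0.

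**The concern.** Multiple imputation relies on data being missing at random given the predictors. Here those predictors say nothing about how a participant responded to the higher dose. Two participants with the same baseline and Week 6 averages, one with high and one with low readings after FU1, get the same predictive distribution if they fall in the same donor group and match on the other covariates.

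Missingness could plausibly depend on that response. High home readings can lead to an urgent visit and add-on treatment (Protocol 8.6); possible hypotension can lead to a change or interruption of treatment (Protocol 8.7). These pressures may differ between triple and dual therapy. Add-on treatment is not a listed intercurrent event in SAP 3.10.1.1, so the donor groups do not separate those participants.

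At stake is the primary contrast. SAP 3.3 requires all three comparisons to succeed. A bias toward zero in one of them could cost the trial its claim; a bias the other way would flatter GMRx2.

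**Working it through.** **1. The plan's own figure.** SAP 2.5 gives 600 vs 300, difference 3 mmHg, SD 11, two-sided 5%.

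- SE = 11 × √(1/600 + 1/300) = 0.778
- 3/0.778 = 3.857, and Φ(3.857 − 1.960) = 97.1% per comparison
- 0.971³ = 91.6% for all three

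Both stated figures (97% and over 91%) reproduce. This point disputes neither.

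**2. Precision.** With many imputations, and data missing at random, the variance of an arm mean is inflated by 1 + [m/(1 − m)] × (1 − R²). Here m is the fraction missing and R² the fit of the imputation model. The documents give no value for m, so 5%, 10% and 15% are assumed. The starting R² of 0.4 is suggested by SAP Appendix 2, which reports values over 40% for mixed models in two similar trials. The values 0.6 and 0.8 are assumed. SD stays at 11, with no credit for baseline adjustment.

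| Missing | Inflation at R² 0.4 / 0.6 / 0.8 | Power per comparison | All three (cubed) |
|---|---|---|---|
| 5% | 1.032 / 1.021 / 1.011 | 96.7 / 96.8 / 97.0% | 90.4 / 90.8 / 91.2% |
| 10% | 1.067 / 1.044 / 1.022 | 96.2 / 96.5 / 96.8% | 89.0 / 89.9 / 90.8% |
| 15% | 1.106 / 1.071 / 1.035 | 95.6 / 96.1 / 96.6% | 87.4 / 88.9 / 90.3% |

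At 10% missing, the interval width ratio is √(1.044/1.067) = 0.99 or √(1.022/1.067) = 0.98, so intervals are 1-2% narrower. Over the whole table the range is about 0.5% to 3%. The largest power gain is 1 point per comparison. At 90% of planned size (540 vs 270) with 15% missing it is 93.6% to 94.9%, or 1.3 points.

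**3. Bias.** A large-sample simulation drew baseline, Week 6 and Week 12 SBP (SD 11 at Week 12) and imputed Week 12 by regression within arm. Baseline and Week 6 explained about 45% of Week 12 variance (0.41/0.914), so the residual SD is 11 × √0.55 = 8.2 mmHg. That residual is the part of Week 12 SBP not predicted from before up-titration. In the dual arm only, the log odds of missingness rose by k per SD of the residual; k = 0.5 and 1 are odds ratios of 1.65 and 2.72. The auxiliary reading had correlation r with the residual.

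| Missing | k | Bias, SAP predictors (mmHg) | r = 0.5 | r = 0.7 | r = 0.85 |
|---|---|---|---|---|---|
| any | 0 | about 0 | about 0 | about 0 | about 0 |
| 5% | 0.5 | 0.20 | 0.15 | 0.11 | 0.06 |
| 5% | 1 | 0.38 | 0.29 | 0.20 | 0.11 |
| 10% | 0.5 | 0.39 | 0.30 | 0.20 | 0.11 |
| 10% | 1 | 0.74 | 0.56 | 0.39 | 0.21 |
| 15% | 0.5 | 0.61 | 0.45 | 0.31 | 0.17 |
| 15% | 1 | 1.06 | 0.81 | 0.57 | 0.31 |

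A rough hand check is m × k × 8.2. For 10% and k = 0.5 this gives 0.41, against 0.39 simulated. The share removed is close to r²: 25%, 49% and 72%.

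**4. Direction and limiting case.** The simulation loses high values from the dual arm, so GMRx2 minus dual moves toward zero. Reversing the sign of k reverses the bias. Opposite patterns in the two arms add. Nearly complete removal needs missingness to depend on the auxiliary itself: a separate 400-replicate run on that assumption (540 vs 270, 9% missing per arm) gave 0.73 mmHg without the late home reading and −0.01 with it.

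**The case against.** The strongest reply is that the simulation is not the SAP's procedure. It has no intercurrent-event groups and no control-based donors, and much dropout driven by blood pressure would fall into those groups. That stands: the bias figures show a mechanism and an order of size, and do not estimate what this trial will see.

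Other points also stand:

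- A home average is missing only if no valid reading exists in seven days, and participants who stop treatment are asked to continue visits (Protocol 8.8). Both limit how much is imputed.
- Clinic SBP helps only those who attend Week 12 without home readings. Interim readings are a soft request and may be sparse in those who drop out.
- The auxiliaries will have gaps of their own, in donor groups that the SAP already expects may be too small.
- For someone who stopped treatment, a reading from before stopping may pull the imputed value toward the on-treatment course, against the aim of using retrieved data. Same-visit clinic SBP does not have this problem.

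The SAP's other analyses do not fill the gap. Supplemental analysis 3 substitutes clinic for home values one for one. Yet Protocol 12.3 cites home reductions about 20% smaller than clinic reductions, and Protocol 10.2.7 does not require clinic readings at trough. A regression would calibrate the two. The tipping point analysis may not be run, and does not shift the dual arms.

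A reader might infer that the primary result is biased, or that the unused readings would remove the bias entirely. The documents support neither. They contain no missing rate, no difference in missingness between arms and no correlation for the auxiliaries, and full removal needs the special case in step 4. Nor may one infer that the plan ignores the higher dose: donors' Week 12 values carry its average effect within each group.

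**Conclusion.** The concern holds as an avoidable weakness in the primary imputation. It is not an arithmetic error or a contradiction. Both blood pressure predictors precede the dose doubling, and readings taken after it are collected but unused there.

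If missingness depends on blood pressure after up-titration, in one arm and with 5-15% missing, the possible bias is about 0.2-1.1 mmHg in either direction. The auxiliaries would remove about 25-70% of it. If missingness does not depend on it, there is no bias. The precision gain is small in any case. The missing rates, odds ratios, auxiliary correlations and R² values above 0.4 are all assumptions. The case for the change is a more credible missing-at-random assumption for the primary result, at low cost.

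**What to change.** Amend SAP 3.10.2.7 before unblinding:

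- **SBP12 model:** add Week 12 clinic SBP and the latest home SBP average recorded after FU1 and before the 7-day Week 12 endpoint window.
- **SBP6 model:** add Week 6 clinic SBP and the latest home average recorded after randomization and before the 7-day Week 6 window.
- **Define the interim average by these dates, not by week number.** Protocol Appendix 3 and SAP Table 3-3 label the endpoint days Week 5 and Week 11. Under the SAP plotting rule Day 77 also falls in Week 11 (77/7 = 11), inside the window before a Day 84 visit. A week label could put part of the outcome among its own predictors.
- **Give each auxiliary its own FCS equation**, since each will have gaps.
- **State the reduction order** for small donor groups or non-convergence: ethnicity, smoking and alcohol first, then the interim home average, keeping same-visit clinic SBP. SAP 3.10.2.7 permits dropping covariates but gives no order.
- **State whether readings from before treatment discontinuation are used** for participants who stopped.

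If the primary model can no longer be changed, prespecify this as a sensitivity analysis. The estimand is unchanged and no new data or visits are needed. The cost is some programming and a somewhat larger imputation model in the small intercurrent-event groups.
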